A pragmatic cluster randomised trial in English secondary schools comparing the impact of a policy of weekly testing for COVID-19 followed by isolation of cases and their contacts, with a policy of weekly testing followed by isolation of cases and daily testing of contacts.

Study Sponsor: Department of Health and Social Care
Principal Investigator: [name]
Co-Investigators: [name], [name], [name], [name], [name]
Chief Data Analyst: [name]
Analyst: [name]

Affiliations

[name]	University of Oxford
[name]	Queen Mary University of London (NHS Test &
	Trace Public Health Lead)
[name]	University of Bristol
[name]	Department for Education
[name]	Department for Education
[name]	Public Health England
[name]	Department of Health and Social Care
[name]	Department of Health and Social Care

Document Approval

Role	Name	Signature	Date
Principle Investigator	[name]	[name]	22/02/2021
Chief Data Analyst	[name]	[name]	23/02/2021

A Note on Definitions

Throughout this protocol the following definitions are used. These are illustrated graphically in Figure 1 below

Index Case	The first known positive COVID-19 case in chain of transmission.
	This individual could be identified asymptomatically via LFD-based active case finding in the school or outside it, or via symptomatic NHS Test and Trace PCR testing
Bubble	Grouping within school created by school to limit transmission of SARS-CoV-2 within the schools. Bubbles are meant to be distinct entities with no intermixing (i.e. a member of Bubble A should have no contact with members of Bubbles B, C, D, etc.)
First-Order Contact	Close contacts of the index case.
	The subset of a bubble identified by the school as being a close contact of an index case, as defined by Government guidance:
	https://www.gov.uk/government/publications/guidance-for- contacts-of-people-with-possible-or-confirmed-coronavirus-covid- 19-infection-who-do-not-live-with-the-person/guidance-for- contacts-of-people-with-possible-or-confirmed-coronavirus-covid- 19-infection-who-do-not-live-with-the-person
	These individuals will be eligible for Daily Contact Testing or self- isolation according to national guidelines (depending on study arm and consent status)
Second-Order Contact	Close contacts of a first-order contact.
	These individuals will be identified and assessed for COVID-19 status in order to measure the secondary attack rate in each arm of the study
Primary Attack Rate	The proportion of first-order contacts of the index case who themselves go on to be diagnosed with COVID-19
Secondary Attack Rate	The proportion of second-order contacts of the index case who themselves go on to be diagnosed with COVID-19

Figure 1: Definitions used for the chain of transmission

1. Rationale

When a person in a school / FE college¹ is diagnosed with COVID-19, first-order close contacts are required to self-isolate for 10 days. In schools, some groups of these close contacts (often managed as 'bubbles') may be quite large (e.g. a whole year group of over 250 pupils) and self-isolation has negative impacts on the education, psychological health and wellbeing of those affected². There is some evidence that suggests that compliance with self-isolation outside the school setting may be as low as 11% in asymptomatic contacts³ (although this may have improved since self-isolation has become a legal requirement). Modelling data shows daily testing of first-order contacts, using rapid lateral flow tests, could avert a similar level of onward virus transmission as self-isolation. In addition, recent work, has found that contacts identified by Test and Trace in the same household are more likely to become infected than first-order contacts at work, school or elsewhere. Primary age children are less likely to infect someone else and contact in schools with an infected child and are at a lower risk of transmission⁴.

It is proposed that when a positive case is detected, first-order close contacts will be offered the choice of being tested daily using rapid Lateral Flow Device antigen testing as an alternative to the requirement to self-isolate. A first-order contact with a negative test at the start of the school day can remain in school. However, they will be advised to self-isolate outside school. A person who tests positive with LFD will follow national protocols and self-isolate for ten days. This process is referred to here as Daily Contact Testing (DCT). DCT will enable the pupil's education to continue and reduced the health and wellbeing impacts of self-isolation.

The success of DCT relies on having a rapid test result. Antigen lateral flow devices (LFD) currently give the quickest result turnaround of all the COVID-19 tests with results available in 30 minutes. Currently NHS Test and Trace has deployed an in-school 'Asymptomatic Testing Site (ATS)' model for LFD testing within schools, where students are tested by a trained workforce (also known as 'assisted testing'). Initial roll-out of LFD-enabled DCT within secondary schools and FE colleges will only be offered at an in-school ATS. Subsequently, at-home self-testing or testing by their parent or guardian ('self testing') may be introduced during the course of the study, conditional on the finalisation of an operational delivery model by NHS Test and Trace, and in agreement with regulators.

As part of the evaluation (rather than as an intervention) a parallel qRT-PCR test will be taken from contacts (by nose and throat, or if this is not tolerated, by anterior nares) to assess how many positive cases are missed by DCT.

¹ Please note that any reference to "school" in this protocol should be taken to include further education colleges also

² Academic Year 2019/20: Schools, pupils and their characteristics. National Statistics.

³ Smith et al. Adherence to the test, trace and isolate system: results from a time series of 21 nationally representative surveys in the UK. September 2020.

⁴ Lee at al. An observational study of SARS-CoV-2 infectivity by viral load and 2 demographic factors and the utility lateral flow devices to prevent 3 transmission. 2021.

2. Evaluation Overview and Objectives

2.1 Study Hypotheses and Objectives

The study hypotheses are as follows:

- 1. That the intervention arm (daily contact testing) will have increased school attendance compared to the control arm (self-isolation) (i.e. superiority)
- 2. That the level of transmission of COVID-19 in the schools in the intervention arm (daily contact testing) is not inferior to (i.e. not higher than in) the control arm (self-isolation)

The primary objective of the study is to assess the effectiveness, in terms of in-school COVID-19 transmission and student / staff in-school days lost to self-isolation, of two different COVID-19 control strategies implemented at a school level using regular active case finding with lateral flow antigen tests.

Both arms of the study will include weekly active case finding of students and biweekly active case finding of staff. The arms will differ in the management of contacts of positive cases:

- (i) Arm 1: routine self-isolation of all first-order contacts of positive tests
- (ii) Arm 2: daily LFD testing of asymptomatic first-order contacts of positive tests at the beginning of the school day with self-isolation restricted to individuals with positive results.

Co-Primary End-Points

- (i) Number of school days lost from COVID-19 or contact with COVID-19 cases
- (ii) Estimated number and rate of within-school COVID-19 transmission events

Secondary End-Points

- (iii) Number and rate of positive contacts missed by daily LFD testing
- (iv) Number and rate of COVID-19 cases transmitted to the school-based and household firstorder contacts of the index case ("primary attack rate")
- (v) Number and rate of COVID-19 cases transmitted to the school-based and household second-order contacts of the index case ("secondary attack rate")
- (vi) Number and proportion of school attendees testing COVID-19 positive in weekly active case finding
- (vii) Proportion of student and staff first-order contacts who accept an offer of daily contact testing with LFD devices

Secondary objectives:

- 1. To gain knowledge on the operational aspects of this process; specifically, to understand uptake and barriers for schools and individuals as well as operational challenges.
- 2. To improve understanding of a range of behavioural factors, including reasons for participating, response to negative and positive test results, and compliance with self-isolation

2.2 This Study in the Context of Overall Evaluation of DCT

An ongoing evaluation of DCT in several settings is ongoing across several dimensions of investigation. This protocol focusses predominantly on the Public Health Effectiveness and Behavioural Factors dimensions, but also touches on the Operational Feasibility and Broader Societal Benefit dimensions. The Scientific Knowledge dimension is not addressed in this study.

The dimensions of the NHS Test and Trace Daily Contact Testing Evaluation Framework can be found in Appendix 1

Within the broader DCT Programme of Evaluation, this study provides the following incremental value:

- 1. It is the first DCT evaluation to include a control arm
- 2. It is the first study to combine dual LFD-PCR swabbing with measurement of participant and institution-level behavioural factors
- 3. It represents a significant expansion of the sample size of previous pilots of DCT in the school / FE college context, allowing for appropriately powered analyses of study endpoints

3.2 Methods

3.1 Overview of Design

This is a pragmatic cluster randomised controlled study. Eligible participating schools will be stratified according to institution type, size, Free School Meal prevalence and local COVID-19 prevalence and randomly allocated into the two study arms. A schematic summarising the study design and participant sub-groups can be found in Figure 2 below.

Regular Active Case Finding. In schools participating in either arm of the study, consent will be obtained from adults/parents/guardians for voluntary weekly testing of all students and biweekly testing of all staff⁵. Tests will be performed with lateral flow devices (LFD)*, and results will be reported in the NHS Test and Trace database. LFD Tests will initially be performed as an assisted test in a school setting. Once a reliable protocol for home testing and recording of LFD is available, schools will be offered the option for at-home self-testing for weekly case finding.

Individuals who test positive will self-isolate and identify first-order contacts according to national guidelines. In addition, symptomatic cases who test positive via NHS Test and Trace, and asymptomatic cases who test positive outside the in-school testing regimen will self-isolate and report their results to the school. All individuals with a positive test will be asked to provide a PCR swab test for genomic sequencing.

1. Intervention (Daily Contact Testing) Arm

a. Public Health Intervention: Consenting first-order contacts of a COVID-positive index case will receive daily contact testing for 7 days from the point of being notified they are a close contact⁶. This will consist of a daily LFD*. Those that receive a negative LFD result can attend school for that day, but other than travelling to and from school will be instructed to continue to self-isolate outside the school setting. Those that receive a positive LFD result should not attend school and will be instructed to self-isolate for 10 days according to national guidelines. The contacts of all first-order contacts (i.e. 'second-order contacts') will be identified to allow the determination of secondary attack rate.

*Daily Contact Testing LFD tests will initially be performed as an assisted test in the school setting. Results will be recorded electronically and reported to NHS Test and Trace. On non-school days participants will not receive LFD testing. Where day 7 of DCT falls on a Saturday or Sunday, a negative LFD test will be needed to exit DCT testing. Once a reliable protocol for home testing and recording of LFD is available, and relevant regulatory approvals are in place, participants may be offered the option for at-home self-test DCT.

Additionally research component: Consenting first-order contacts will be tested via self-administered qRT-PCR at days 2 and 7 from the point of being notified they are a

⁵ Biweekly LFD active case finding among staff is already underway outside the context of this evaluation

⁶ For clarity, the day on which they are notified they are a contact is Day 0

close contact⁶. These qRT-PCR samples will be collected for research purposes and run in batches every two weeks, after which results will be available for participants.

2. Control Arm

- Public Health Intervention: First order contacts of a COVID-positive index case will be instructed to self-isolate according to national guidelines (i.e. there will be no change to the public health intervention compared to non-participation in the evaluation). The contacts of all first-order contacts (i.e. 'second-order contacts') will be identified to allow the determination of secondary attack rate.
- b. Additionally research component: Consenting contacts will be provided with two home qRT-PCR test kit and asked to self-test at days 2 and 7 from the point of being notified they are a close contact⁶. These qRT-PCR samples will be collected for research purposes and run in batches every two weeks, after which results will be available for participants.

Figure 2: Schematic of study design and participation sub-groups

Consideration was given to a stepped-wedge study design where schools would introduce daily contact testing in waves. This was not pursued as part of this protocol due to the operational feasibility of this design.

Consideration for comparator testing regimes and groups of varying prevalence as part of the evaluation were considered but will not be part of this phase.

3.2 Inclusion and Exclusion Criteria for Schools

- Inclusions
 - o Secondary school / further education college
 - Willing and able to follow the study protocol
 - Willing and able to undertake PCR testing of contacts in the event the school is allocated to the control group
 - o Commits to maintain contact management in line with national standards
 - Willing and able to provide regular data of test results to Test and Trace and to allow members of an index case's contact group to be flagged in a data base.
 - Willing and able to support baseline data collection requirements (e.g., provision of school register, bubble allocation data, etc.)
 - Willing to communicate regularly to Participants via Participant Information Sheets and other communication materials
 - Willing and able to provide a dedicated DHSC-funded Research Assistant to support data collection
- Exclusions
 - \circ $\;$ The school's contact management policy does not conform to national standards
 - Inability to support in-school LFD testing (i.e. not part of the NHS Test and Trace Asymptomatic Testing Site network)

3.3 Non-Consenting Individuals in the Interventional Arm

Within the intervention arm, individuals not participating in DCT will self-isolate in the event they are a first-order contact. They will be asked to participate in elements of the qualitative work to enable better understanding of factors affecting uptake and pre and post-test behaviours.

3.4 Lateral Flow Device Testing

LFD antigen testing will be via two delivery models:

- 1. Supervised anterior nares swabbing, and device use within a school's 'Asymptomatic Testing Site (ATS)' model. The workforce for this will be trained according to national NHS T&T standard process.
- 2. Home or Self-testing will be made available once reliable operational delivery models are developed, and subject to the relevant regulatory approvals being received.

3.5 qRT-PCR Testing

The purpose of the qRT-PCR test component is to determine the number of first-order contacts which are positive with PCR but negative with LFD during DCT. This will determine the false negative rate of DCT. First-order contacts will be prioritised in the daily testing schedule in the school to ensure they are tested at the beginning of the day.

The swabbing method for qRT-PCR swabbing will be throat-and-nose as per standard NHS T&T practice. If throat-and-nose swabbing is not tolerated, anterior nares swabbing may be used. Schools / participants should record which swabbing method is used each day. Participants should self-swab under supervision in alignment with national NHS T&T guidance.

qRT-PCR swab samples will be transported to PHE Porton Down, stored at -20°C and processed in batches every two weeks. Results will be available to participants after this time. This process is being implemented to prevent participants (in either stud arm) from receiving information on their COVID-19 status that they will not receive as part of the real-world public health intervention. This will be communicated to potential participants via the Participant Information Leaflet and ICF prior to enrolment in the study.

qRT-PCR testing will not form part of scaled LFD-enabled testing of asymptomatic close contact groups in schools. As such, the evaluation framework for the study will not consider the acceptability, tolerability or operational performance of the qRT-PCR testing component.

3.6 Assessment of End-Points

Please see the glossary at the start of this protocol for definitions

Co-Primary End-Points

(i) Number of school days missed among those eligible to be in school.

Daily school attendances will be obtained from the school register and absences recorded with reconciliation with COVID-19 associated absences. This will be compared between study arms, to historic schools' data, and to national schools' benchmark data collected via a survey of non-participating schools.

(ii) Estimated number of in-school COVID-19 transmission events

The number of positive cases will be obtained from the following sources:

- 1. Weekly LFD active case finding (Control and Intervention Arms)
- 2. Symptomatic individuals' NHS Test and Trace results obtained from Community Testing routine data (Control and Intervention Arms)
- 3. In-school LFD DCT testing (Interventional Arm).

Positivity rates will be reported for each source separately to facilitate like-for-like comparison between arms

Epidemiological links between cases will be obtained from the NHS Test & Trace Contact Tracing and Advice Service data base. Additional links will be obtained by membership of school-reported contact groups. Onward transmission from the index case will be determined by the following:

• Genomic sequence of virus: The additional PCR swab collected from positive individuals will be used to determine the whole genomic sequence of isolates. A sample of apparent links will be assessed with comparisons of whole genome sequencing. The diversity of genetic sequences both in the schools and the

community (routinely determined by COG) will be used to help interpret the results. Preliminary work currently undertaken will determine the appropriate genetic distance to be used to exclude a direct transmission event between individuals. This is likely to be 2 SNPs.

- Plausible epidemiological link (e.g. membership of same close contact group)
- For positive individuals identified in DCT the DMIC will review all available data to determine if the individual's infection was likely to have resulted from onward transmission from the index case, or via co-infection from an unknown 'upstream' positive or out-of-school positive case.

Secondary End-Points

(iii) Number of positive first-order contacts missed by daily LFD testing (Intervention arm only).

Routine qPCR of first-order contacts will be used to determine the performance of DCT testing with LFDs. Comparisons of PCR with the same day LFD will allow comparison between CT values and LFD results in a 'real world setting' These comparisons can also be used to compare the relative performance between assisted school-based testing and home/self-testing.

(iv) Number of COVID-19 cases transmitted to the first-order contacts of index cases ("primary attack rate").

The first-order close contacts of all index cases will be identified by the school based on their existing close contact management policy. LFD DCT testing and (for symptomatic individuals) routine NHS Test and Trace PCR testing will be used to calculate primary attack rate.

As above, genomic sequencing will be used, wherever possible, to exclude non-direct transmission events.

(v) Number of COVID-19 cases transmitted to the second-order contacts of index cases ("secondary attack rate").

The second-order contacts of all index cases will be identified (regardless of the COVID-19 status of the DCT-contacts) as described in Section 3.7. The COVID-19 status of these second-order contacts will be measured in two ways:

- i. Where the second-order contact is a consented participant in this study their COVID-19 status will be assessed by weekly LFD active case finding, and records kept by the school of any participants who become symptomatic and test positive via standard NHS Test and Trace community testing.
- ii. Where the second-order contact is not a consented participant in this study (e.g., household contact of first-order contact), analysis of routine NHS Test and Trace data will be used to determine if they subsequently become symptomatic and test positive in the community setting.

As above, genomic sequencing will be used, wherever possible, to exclude non-direct transmission events.

(vi) Number and proportion of school attendees testing COVID-19 positive in weekly active case finding.

LFD results and school attendance registers will be used to calculate active case finding rate. This will be compared between study arms, and to national schools' benchmark data collected via a survey of non-participating schools.

(vii) Proportion of student and staff who accept an offer of weekly active case finding testing with LFD devices.

Schools will maintain consenting records to allow participation rates to be calculated.

(viii) Proportion of student and staff first-order contacts who accept an offer of daily contact testing with LFD devices.

Schools will maintain consenting records to allow participation rates to be calculated.

(vii) Behavioural outcomes for pupils, parents and staff: acceptability and feasibility of testing, self-reported perceptions and behaviour

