The number of Covid-19-associated missed days at school is dependent on the number of positive cases identified and the number of contacts of these cases that are self-isolating. Each positive case is self-isolated for 10 days. In the control group all first order contacts will also be self-isolated for 10 days. It is expected that this trial will occur in the summer term when the number of cases in a school will be low. For instance, it is expected that in the control group about 30% of children (and their parents) will consent to participate in regular weekly active case finding testing. For the purposes of the power calculation, it is assumed that the expected number of index cases identified is about 1 outbreak/month. Each index cases will lead to identification of 50 children in their bubble who will need to self-isolate each for 10 days. The number of index cases identified is a Poisson distribution with mean 1/month with each index cases leading to 510 missed school days.

In the intervention group, it is expected that a more complex set of interactions will occur. The ability to avoid self-isolation by DCT is likely to make participation in weekly active case finding testing more

⁸ Quartagrio et al, 'Handling an uncertain control group event risk in non-inferiority trials: non-inferiority frontiers and the power-stabilising transformation' (2020)

attractive with an increase in consent to voluntary weekly active case finding testing to 60%. This in turn will lead to the identification of more positive cases with initially an expected number of 2 different index cases identified per week. However, it is expected that 70% of children will volunteer for DCT and therefore only 15 children (25% of 50) will self-isolate. In addition, about 2 contacts will be identified by LFD testing as positive during DCT (5% of 35). It is expected that these 2 children will only have contacts within the bubble and therefore they will not lead to identification of more children. In all, each index cases will lead to the index cases or 360 missed schools / month

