4.1.2 Positive LFD Result

- The school should follow the national guidance (link above), in the same way as if the person with the positive test had become symptomatic whilst in school. The person in question must begin self-isolation in accordance with national guidance and Stay at Home guidelines¹⁰.
- Residential schools must follow the national guidance for residential educational settings: https://www.gov.uk/government/publications/coronavirus-COVID-19-guidance-on-isolation-for-residential-educational-settings/coronavirus-COVID-19-guidance-on-isolation-for-residential-educational-settings.
- Participants testing positive will be given a home PCR testing kit. They should be instructed to take a PCR swab **that day** and return it as per the enclosed instructions. This sample will be subject to genomic sequencing to allow chains of transmission to be analysed.

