5.3 Results Data Monitoring

During the trial the combined results of all schools in the trial will remain blinded to all except the statistical centre and the Independent Data Monitoring Committee (IDMC). The IDMC will review the overall quality, safety and efficacy of the data and make recommendations to the Trial Steering Committee on whether the trial protocol should be altered. If they have evidence beyond reasonable doubt that one strategy is clearly superior (or inferior) to another arm and that the result is likely to change public health practice, they should immediately report the unblinded data and their recommendation to the Trial Steering Committee.

Statistical Analysis of primary and secondary end-points

Conventional statistical analysis will be undertaken. Analysis will be undertaken for the primary objective at a per-school basis with comparisons to the population of control schools. Absent school days (both total and COVID-related) will be presented as a proportion of pupils (with binomial confidence intervals). Unadjusted transmission events will be measured as the incidence of all COVID-19 positive cases determined by both Pillar 2 and school directed testing. Transmission events will also be categorised as 'more likely' if they either have a similar genetic sequence (the cut off to be determined) or as a member of the same predefined school bubble.

Secondary analysis

The performance of DCT will be made at the level of each primary contact. The performance of the DCT will be compared to PCR using conventional exact binomial statistics. The extent of secondary transmission events will be analysed using Poisson statistics and the results

stratified according to the LFD and PCR results of the DCT-contact. The results can also be adjusted according to the day that the LFD becomes positive and the CT value of the PCR result.

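### The transmission endpoints count lateral flow positives as COVID-19 cases without PCR confirmation, although a same-day PCR is already requested from each one

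*Protocol*

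**What the plan says.** Section 3.6 lists the case sources for co-primary (ii). The first is "Weekly LFD active case finding (Control and Intervention Arms"), the second is symptomatic Test and Trace results, and the third is "In-school LFD DCT testing (Interventional Arm"). Section 5.3 gives the counting rule: "Unadjusted transmission events will be measured as the incidence of all COVID-19 positive cases determined by both Pillar 2 and school directed testing". It adds a more-likely category, reached by a similar sequence "or as a member of the same predefined school bubble".

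The definitions at the front of the protocol allow an LFD positive to be the index case: "This individual could be identified asymptomatically via LFD-based active case finding in the school or outside it". Section 4.2 confirms that a weekly LFD positive triggers management of first-order contacts. In section 3.6 the primary attack rate (iv) uses DCT LFD results, plus PCR for symptomatic contacts. The secondary attack rate (v) uses weekly LFD results for consented participants.

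On PCR, section 3.1 says: "All individuals with a positive test will be asked to provide a PCR swab test for genomic sequencing". Section 4.1.2 gives its use after a weekly LFD positive: "This sample will be subject to genomic sequencing to allow chains of transmission to be analysed". Section 4.2.1 says the same for DCT positives. Nothing in the protocol says how an LFD-positive, PCR-negative person is classified.

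On prevalence, section 3.9 states: "It is expected that this trial will occur in the summer term when the number of cases in a school will be low".

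**The concern.** When infection is rare, even a very specific test produces false positives in numbers comparable with true ones. Under the stated rule each is counted as a case. If it is the first positive in its group it also becomes an index case, and brings in a group of first-order contacts whom it did not expose. A PCR-negative swab yields no sequence, so genetic distance cannot exclude the person, while shared bubble membership is enough to place the event in the more-likely category.

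Randomisation does not balance the error. The intervention arm is expected to have higher weekly uptake (60% against 30%) and alone runs DCT LFDs. Section 3.9 sets no non-inferiority margin and asks an independent committee to judge the confidence interval for the difference in transmission. Misclassification that differs by arm goes straight into that judgement.

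**Working it through.** **Inputs from section 3.9 and Table 1.** Weekly uptake is 30% (control) and 60% (intervention, upper end of 40–60%). Detected outbreaks are 1 and 2 per school-month. Each index case has 50 contacts, 70% take up DCT (35), and about 2 of them test positive. Table 2 assumes a two-month study.

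**The plan's own figures.** Control: (1 + 50) × 10 = 510 missed days per index case, as stated. Intervention: 2 index cases × (1 + 15 + 2) × 10 = 360 per month, as stated. The 360 confirms that the rate used is 2 per month, as in Table 1, although the text of 3.9 says per week. Over two months this gives 2 and 4 index cases per school. Table 2's entry of 58 schools per arm (15 isolating, 60% uptake) also reproduces, using a compound Poisson model and a noncentral t. It concerns attendance and is not in dispute.

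**Assumptions, not in the protocol.** 600 to 1,250 pupils; false-positive rate 0.0003 to 0.001 per test; 8 weekly rounds; 5 school-day tests per DCT contact. Staff tests are left out.

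**False positives from weekly testing, per school over two months** = pupils × uptake × 8 × false-positive rate.

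| | Control, 30% | Intervention, 60% |
|---|---|---|
| Tests, 600 pupils | 600 × 0.3 × 8 = 1,440 | 600 × 0.6 × 8 = 2,880 |
| Tests, 1,250 pupils | 1,250 × 0.3 × 8 = 3,000 | 1,250 × 0.6 × 8 = 6,000 |
| Lowest false positives | 1,440 × 0.0003 = 0.43 | 2,880 × 0.0003 = 0.86 |
| Highest false positives | 3,000 × 0.001 = 3.0 | 6,000 × 0.001 = 6.0 |
| Planned detected outbreaks | 2 | 4 |

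**False positives from DCT.** Tests in uninfected contacts per index case: 33 × 5 = 165. Times 0.0003 to 0.001 gives 0.05 to 0.17, against about 2 expected positives. Over 4 index cases this is 0.20 to 0.66 per school, in the intervention arm only.

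**Excess in the intervention arm.** Low: (0.86 − 0.43) + 0.20 = 0.63. High: (6.0 − 3.0) + 0.66 = 3.66 per school over two months.

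**Cross-check at 1,000 pupils and 4.33 weeks per month.** At 0.03%: control 300 × 4.33 × 0.0003 = 0.39 per school-month, against 1 planned. Intervention 600 × 4.33 × 0.0003 = 0.78, plus 0.10 from DCT (2 × 35 × 5 tests), against 2 planned. At 0.1% the totals are 1.30 and 2.95. At a poorer 0.5% they are 6.5 and 14.7.

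**Predictive value of a weekly positive** (assumed prevalence 0.1%, sensitivity 50% to 70%). PPV = prev × sens / [prev × sens + (1 − prev) × false-positive rate]. This gives 0.63 to 0.70 at 0.03% and 0.33 to 0.41 at 0.1%.

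**Direction.** In (ii), more false positives fall in the intervention arm, so its apparent incidence rises. In (iv) and (v), contacts of a false index case enter the denominator with no exposure from that case, which lowers the rates. False LFD positives among contacts raise them again. In (iv) this happens essentially in the intervention arm alone, because control contacts are assessed by symptomatic PCR.

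**The case against.** Only the protocol is at hand, and handling of discordant LFD and PCR results could sit in a statistical analysis plan. That is fair as far as it goes. However, the protocol itself fixes the case sources, the counting rule and the purpose of the PCR, and followed as written these count false positives.

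The protocol also has safeguards. Positivity is reported by source, some suspected links are sequenced, a committee reviews DCT positives, and section 5.3 stratifies secondary transmission by the contact's LFD and PCR results. These help, especially for DCT. But they address who infected whom, or describe the streams separately. None removes an uninfected LFD positive, and none applies to a false index case from weekly testing. The day 2 and day 7 PCRs cover contacts only and are meant to find DCT false negatives (section 3.5).

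In a pragmatic comparison of policies, an LFD positive is what triggers action, so keeping policy-defined index cases is defensible. That stands. It is why removing whole contact groups belongs in a sensitivity analysis, the more so because return of a voluntary home swab may differ by arm.

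Several stronger readings are tempting but unsupported:

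- **Every LFD positive is an index case.** The definition is the first known positive in a chain; a DCT positive is a case among contacts.
- **A PCR is in hand for each positive.** It is requested, using a home kit.
- **The bias favours a finding of non-inferiority.** In (ii) it runs against the intervention.
- **Arm differences in attack rates are halved if half the index cases are false.** This ignores false positives added by DCT. Take true rates of 5% (control) and 6% (intervention), and a 0.1% false-positive rate over 5 tests. Control reads 2.5%. Intervention reads 3.0% plus about 0.5 points among tested contacts, or 0.35 points over all contacts at 70% uptake. The gap is 0.85 to 1.0 point, against a true 1.0.
- **Endpoint (vi) is wrong.** It is weekly LFD positivity by definition and is compared with external benchmark schools.

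**Conclusion.** The point holds in limited form. Endpoints (ii), (iv) and (v) count LFD positives with no role for the PCR already requested, and the resulting error is unequal between arms. Under the stated assumptions, weekly testing gives about 0.4 to 3.0 false positives per control school and 0.9 to 6.0 per intervention school over two months. DCT adds 0.05 to 0.17 per index case.

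The size is uncertain. Specificity and school size are both assumed, and the result varies about sevenfold across their range. Table 1 counts detected outbreaks, which may already include false positives. The comparison with 2 and 4 therefore shows scale and is not a share; at the upper end, false positives alone would exceed the planned total.

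The net direction is not fixed: incidence in (ii) is pushed against the intervention, while dilution of (iv) and (v) works towards no difference and DCT false positives work the other way. The attendance endpoint and its sample size are untouched, because days lost after a false positive are real absences.

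**What to change.** For endpoint classification only, with isolation and contact-management rules unchanged:

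- In (ii), (iv) and (v), do not count an LFD positive as a case or transmission event if the same-day PCR, and any other PCR in that episode, is negative.
- Keep LFD positives with no returned PCR in the main count, labelled unconfirmed, with a sensitivity analysis that removes them. Report PCR return by arm.
- Report the count of all LFD positives as a supporting analysis.
- Repeat (iv) and (v) without the contact groups of PCR-negative index cases, as a sensitivity analysis.
- Leave (vi) as LFD positivity so that the benchmark comparison holds, and give the PCR-confirmed proportion beside it.

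The cost is protocol wording and linkage of PCR results to LFD episodes; no new swab is needed. The downside is that a few true cases with a poor home swab are lost from the main count. The supporting analysis of all LFD positives still includes them.
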